- g PK blood samples should be drawn pre-and post- - infusion on Day 1 and Day 3. The end of infusion PK draw should be drawn within 10 minutes after the end of infusion and the ECG should be \pm 10 minutes from the PK draw.
- h The ECGs will be collected in triplicate pre- and post-infusion as close to PK draws as possible. The end of infusion PK draw should be drawn within 10 minutes after the end of infusion and the ECG should be \pm 10 minutes from the PK draw. A 12-lead ECG recording will be conducted using an ECG machine that automatically calculates the heart rate and measures PR, QRS, QT, and QTcF intervals.
- i AE/SAE collection will occur through 30 days post SBRT completion for treatment related adverse events, will continue through 90 days post SBRT completion for acute toxicities (all AEs/SAEs) and 1-year post SBRT completion for late radiation toxicities. Please see [Section 7.4](#) for the definition of late radiation toxicities. The DLT period is through 30 days post-SBRT for Phase 1 subjects. Please see [Section 7.5](#) for details on the DLT definition.
- j All medications taken from 30 days prior to dosing through 90 days post SBRT completion should be documented in source records and CRF. After 90 days post-SBRT, only medications used to treat late radiation toxicities should be recorded through 12 Months post SBRT completion, including inhalers, steroids, oxygen supply, etc. Additionally, any new anti-cancer therapy given in follow-up should be recorded in the CRF through 24 months post-SBRT or disease progression.
- k Imaging assessments performed as part of standard of care within 56 days of dosing will be accepted. Investigator Response Assessment should follow RECIST 1.1. Suspicion of progression should be confirmed with PET at 6 months. Radiographic assessment of pneumonitis will occur by evaluating for presence of descriptors listed in the table in Appendix 4.
- l GC4711 or placebo will be given prior to each dose of SBRT starting the first day of SBRT through the last day of SBRT. GC4711/placebo infusion should be completed within 180 minutes prior to the start of SBRT. For patients treated with a 3-fraction SBRT regimen, only 3 doses of GC4711 will be administered.

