Secondary	
- To determine the degree of in-field tumor response at 6, 12, 18 and 24 months following completion of SBRT- To compare progression-free survival, overall survival, local tumor control, and distant metastasis rates over a 2-year follow up period for SBRT plus GC4711 or placebo- To assess durability of in-field complete or partial responses- To determine acute lung toxicity after SBRT + GC4711 compared to SBRT + placebo for early-stage NSCLC- To evaluate the rate of acute and late radiation toxicities for SBRT + GC4711 compared to SBRT + placebo- To assess the relationship between clinical, functional and radiographical lung function changes observed after SBRT 
- Percent reduction of in-field tumor at Months 6, 12, 18 and 24- Number of participants with CR+PR- Number of participants experiencing grade 1 or higher in diffusion capacity of lung for carbon monoxide (DLCO), measured by RTOG scale, at 6-months after the completion of SBRT- Measurement of the following parameters over 12 months after SBRT
- Changes in pulmonary function testing (pulse oximetry [SpO₂], forced vital capacity [FVC], first expiratory volume in the first second [FEV₁], DLCO), clinical and radiological pneumonitis scoring- Reporting of observed adverse events in patients- Late Radiation Toxicities (including clinical and radiographic pneumonitis, esophagitis, pulmonary fibrosis, rib fractures, plexopathy, cardiac and vascular events) up to 12 months following the completion of SBRT- Measurement of the following parameters over 24 months after SBRT
- Progression Free Survival (PFS)- Overall Survival (OS)- Local and regional control- Distant Metastases (DM) rate

OBJECTIVES	ENDPOINTS
	-

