5.1 Inclusion Criteria

Participants are eligible to be included in the study only if all the following criteria apply:

1. Male or female subjects at least 18 years of age.
2. Ability to understand and the willingness to sign a written informed consent.
3. Histological or biopsy proven NSCLC. For peripheral lesions, cytology and/or clear imaging-guided suspicion is accepted if histology cannot be obtained.
4. ECOG performance status of 0-3.
5. Lymph node negative (T1 to T3N0M0), centrally located (within 2cm in all directions around the proximal bronchial tree, including ultra-central tumors, abutting the bronchial tree or trachea) or large (>1-7cm) Non-Small Cell Lung Cancer (NSCLC) , judged acceptable for SBRT by the treating Investigator. Staged with FDG-PET/CT, brain CT or MRI with contrast and/or mediastinoscopy, measurable disease as defined by RECIST 1.1. (See Figure 2 below).
6. Adequate end-organ function, based on routine clinical and laboratory workup:
 - a. ANC >1,000 cells/ μ l, Platelets \geq 75,000 cells/ μ l, Hemoglobin \geq 8.0 g/dl
 - b. Serum creatinine \leq 2 mg/dL or calculated creatinine clearance \geq 30 ml/min
 - c. Total bilirubin \leq 1.5 x ULN (or direct bilirubin below the ULN), AST and ALT \leq 2.5 x ULN
 - d. International normalized ratio (INR) (or prothrombin time (PT)) and activated partial thromboplastin time (aPTT) \leq 1.5 x ULN unless participant is receiving anticoagulant therapy, if values are within the intended therapeutic range
7. Males and females of must agree to use effective contraception starting prior to the first day of treatment and continuing after the last dose of GC4711/Placebo for 30 days (females) and 90 days (males).

[figure not shown]

Figure 2 Anatomy of central and ultra-central lung tumors

Timmerman and colleagues defined central lung tumors as those located within 2 cm of the proximal bronchial tree (Timmerman 2006). Here defined ultra-central lung tumors as those abutting the proximal bronchial tree or trachea (Lo 2010, Chaudhuri 2015, Chang 2018).

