8 STATISTICAL CONSIDERATIONS

8.1 Sample size

In Phase 1 of the study, 5 patients will be treated with GC4711 in combination with SBRT. Dose limiting toxicity (DLT) is defined in Section 7.5. Safety is considered acceptable and confirmed in the Phase 1 portion of the study, if DLT occurs in no more than one of the first five DLT-evaluable patients.

If acceptable safety in Phase 1 is confirmed, Phase 2 will proceed. Approximately sixty-six (66) participants, randomized 1:1 to GC4711 or placebo, will be recruited for the Phase 2 portion to achieve 60 evaluable subjects, assuming an approximate 9% drop out rate prior to the 90-day timepoint evaluation.

The primary objective in Phase 2 is to estimate the difference in in-field tumor response between GC4711 and placebo through Month 6 following SBRT. Sample size in Phase 2 is selected to provide a reasonably precise estimate of the treatment effect as measured by the width of a two-sided 90% confidence interval around the difference in in-field tumor response as well as to provide other efficacy data that can be used in planning future studies. With 30 patients/arm the half-width of the 90% confidence interval for the difference will be at most 21.2% based on the large sample confidence interval with limits $\pm Z.05 \sqrt{[(p1*(1-p1)/n + p2*(1-p2)/m)]}$ of the point estimate where p1 and p2 are the response rates and n and m the corresponding number of patients in each arm.

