8.5 Statistical Analyses

The statistical analysis plan will be finalized prior to database lock and will include a more detailed description of the statistical analyses described in this section. Should the statistical analysis plan and the protocol differ with respect to analytic conventions, the statistical analysis plan supersedes the protocol. Given the study has not been powered for formal hypotheses testing, all P-values should be considered descriptive in nature. As such no alpha adjustment for multiple testing is planned.

All time to event endpoints will be measured from date registration (Phase 1) or randomization (Phase 2).

Primary Endpoints:

Phase 1: DLT defined in Section 7.5.

Phase 2: The difference in in-field tumor response between GC4711 and placebo through Month 6 following SBRT will be estimated, and a two-sided 90% confidence interval constructed around the difference using the large sample confidence interval with limits $\pm Z.05 \sqrt{[(p1*(1-p1)/n + p2*(1-p2)/m)]}$ of the point estimate where p1 and p2 are the response rates and n and m the corresponding number of patients in each arm. In addition, a Fisher's Exact test will be performed but should be considered descriptive in nature. Phase 2: Percent reduction of in-field tumor response at Month 6 compared to baseline.

Secondary Efficacy Endpoints:

Phase 1: All Phase 1 efficacy endpoints will be summarized descriptively.

Phase 2: Response rate (PR+CR at any time during the study) per RECIST 1.1 will be compared using the same methodology as the primary endpoint.

In-field tumor response at Months 6, 12, 18 and 24 will be compared for the two treatment arms using a t-test at each timepoint and corresponding two-sided 90% confidence intervals constructed about the difference. The maximum reduction for each patient observed at any time will be analyzed similarly.

Progression-free survival (PFS) will be compared using a hazard ratio along with the associated 2-sided 90% confidence interval, using an un-stratified Cox's proportional hazard model and further characterized by Kaplan-Meier curves as well as the median and survival probability at

representative times (e.g. at 2, 4, 6, 4 etc. months). A log-rank test comparing treatment arms based on the score statistic from the Cox regression will also be provided. Patients who have not progressed or died will be censored at their last evaluable response assessment.

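### Baseline tumour diameter is measured but not used as a covariate in the in-field percent-reduction t-tests or alongside the primary response difference; prespecifying it costs about 1% of interval width at worst

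*Combined protocol and SAP*

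**What the plan says.** Section 3 lists, as a Phase 2 secondary endpoint, "Percent reduction of in-field tumor at Months 6, 12, 18 and 24". Section 8.5 (Secondary Efficacy Endpoints) gives the method: "In-field tumor response at Months 6, 12, 18 and 24 will be compared for the two treatment arms using a t-test at each timepoint", with two-sided 90% confidence intervals. The maximum reduction per patient is handled in the same way. I read the t-tests as applying to percent reduction, since a t-test needs a continuous variable and Section 3 supplies one.

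For the primary endpoint, Section 8.5 says the difference in response rates "will be estimated, and a two-sided 90% confidence interval constructed around the difference using the large sample confidence interval", with a descriptive Fisher's exact test beside it. No covariate is named for either analysis.

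Section 8.1 chooses the sample size by precision, "as measured by the width of a two-sided 90% confidence interval around the difference in in-field tumor response", and states: "With 30 patients/arm the half-width of the 90% confidence interval for the difference will be at most 21.2" percent.

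Other relevant points:
- Section 7.1 (Tumor Assessment) defines partial response against the baseline sum of diameters, so baseline diameter must be measured.
- Section 5.1 admits lesions described as "large (>1-7cm) Non-Small Cell Lung Cancer (NSCLC"), and admits central tumours by location.
- Section 8.2 describes allocation through an RTSM system and names no stratification factor.
- Section 8.7 plans an unblinded look at efficacy once the first 20 randomised subjects have 6-month data.
- Section 8.5 says a more detailed SAP will be finalised before database lock and will supersede the protocol on analytic conventions.

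**The concern.** The Phase 2 part is an estimation study. P-values are descriptive, and interval width is the only stated justification for the sample size. An available baseline variable that might tighten the intervals is therefore directly relevant.

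The synopsis links larger and central tumours with worse local control, so the sponsor itself regards size as plausibly prognostic. With about 30 evaluable patients per arm and no stated stratification by size, the arms could differ by chance in tumour size. If size affects shrinkage or response, the unadjusted estimates would carry that difference.

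Two things are at stake: some precision in the percent-reduction comparisons, and protection of both estimates against a chance imbalance. Timing matters too. A covariate chosen after the unblinded look would be open to the criticism that the data guided the choice.

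**Working it through.** **Inputs from the documents.** 30 evaluable per arm (Section 8.1), about 33 per arm randomised (synopsis), two-sided 90% intervals (z = 1.645), size range just over 1 to 7 cm (Section 5.1). **Assumed, because the documents give no value:** the within-arm correlation ρ between percent reduction and baseline diameter, the dependence of response on size, and the spread of diameters.

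**1. The plan's own figure.** 1.645 × √(0.25/30 + 0.25/30) = 0.2123, or 21.2 points. It reproduces, and it is the correct worst case for the unadjusted interval.

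**2. Percent reduction: ANCOVA against t-test.** The t-test half-width is t58 × √(2/30) = 0.432 SD. Adding one covariate gives

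ratio = (t57/t58) × √[(1 − ρ²)(1 + 1/56)].

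Patient equivalents are 1/ratio² − 1.

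| ρ | ratio | change in width | equivalent extra patients |
|---|---|---|---|
| 0 | 1.009 | 0.9% wider | none |
| 0.1 | 1.004 | 0.4% wider | none |
| 0.2 | 0.989 | 1.1% narrower | 2% |
| 0.3 | 0.963 | 3.7% narrower | 8% |
| 0.4 | 0.925 | 7.5% narrower | 17% |
| 0.5 | 0.874 | 12.6% narrower | 31% |

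A separate 5,000-replicate simulation gave 1.009, 0.963, 0.924 and 0.875 at ρ = 0, 0.3, 0.4 and 0.5. The ratio crosses 1 between 0.1 and 0.2, so a correlation near 0.15 is needed before there is any gain.

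**3. Primary: standardised against raw risk difference.** 4,000 simulated trials per row, 30 per arm, no treatment effect, overall response 50%, diameter uniform on 1–7 cm. The adjusted estimate comes from a logistic model with arm and diameter, averaged to a risk difference. Half-width = 1.645 × simulated SD, in points. The last column is the size of the shift in the raw difference caused by a 0.5 cm difference in mean diameter.

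| response at 1 cm / 7 cm | unadjusted | adjusted | shift per 0.5 cm imbalance |
|---|---|---|---|
| 50 / 50 | 21.1 | 21.2 | about 0 |
| 60 / 40 | 21.0 | 21.0 | 1.6 |
| 70 / 30 | 21.1 | 20.6 | 3.5 |
| 80 / 20 | 21.3 | 20.0 | 5.4 |
| 90 / 10 | 21.1 | 18.2 | 7.5 |

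The gain is 0 to 1.3 points, except in the last row, where size almost decides response.

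**4. Chance imbalance.** The difference in baseline means has SD √(2/30) = 0.258 baseline SDs. P(|difference| ≥ 0.3 SD) is 24.5% at 30 per arm and 22.3% at 33 per arm. In centimetres, the chance of a mean difference above 0.5 cm is 5%, 20% or 26% for an assumed diameter SD of 1.0, 1.5 or 1.73 cm. At the interim look, if the split is 10 per arm, the SD of the difference is √(2/10) = 0.447, and a 0.3 SD imbalance has about a 50% chance.

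**The case against.** The strongest reply is that nothing here is wrong. The unadjusted difference is valid under randomisation, and its interval already allows for chance imbalance. Both endpoints are scaled to baseline. The study is descriptive, and the later SAP could add covariates. Every benefit figure rests on an assumed association; the remark about worse local control in larger or central tumours concerns neither percent shrinkage nor RECIST response. All of this stands, and it limits the point to an improvement. It does not remove the point, because the cost is so small and because width is the plan's own criterion.

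A reader might infer stronger versions that the documents do not support:
- *That the plan ignores baseline size.* It does not: percent reduction and the 30% threshold are both relative to baseline. Only the covariate is absent.
- *That adjustment always narrows the interval.* Below a correlation of about 0.15 it does not.
- *That reading error, larger in percent terms for small tumours, makes adjustment pay.* That makes the variance depend on size, whereas ANCOVA adjusts the mean. With 2 mm error and true shrinkage unrelated to size (mean 30%, SD 25 points, all assumed), the induced correlation is only about 0.03–0.04 and the width ratio 1.008. At 3 mm it is 0.07–0.10 and 1.004.
- *That scan age should be a covariate too.* Table 1 says only that standard-of-care imaging "within 56 days of dosing will be accepted"; capture of the scan date is not stated and no benefit has been shown. If scan age is unrelated to outcome, the two-covariate model gives a ratio of about 1.013–1.018.
- *That randomisation is known to be unstratified.* Section 8.2 is silent. The plan applies that word only to the Cox model.

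**Conclusion.** The point holds as a recommended, nearly free improvement, chiefly for the percent-reduction analyses. It is not an error in the plan, and the 21.2-point figure needs no correction.

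For percent reduction, the worst outcome is an interval about 1% wider. Under moderate correlations of 0.3 to 0.5 it would be about 4% to 13% narrower, worth about 8% to 31% more patients. For the binary primary, the precision gain is small, and protection against a chance size imbalance is the better reason for a supportive adjusted estimate. That protection has value only if size is prognostic.

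That neither analysis uses the covariate is plain from Section 8.5. The size of the benefit is not known, because the documents report no correlation between diameter and shrinkage and no gradient of response with size. The calculations also use 30 per arm at every visit. Section 4.2 requires no tumour assessments after progression, so later visits will have fewer patients, who may be less well balanced on size.

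**What to change.** In the SAP, before the unblinded interim look in Section 8.7:

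1. **Percent reduction at Months 6, 12, 18 and 24, and maximum reduction.** Make the main analysis an ANCOVA with arm and baseline in-field diameter, reporting the adjusted difference with a two-sided 90% confidence interval. Keep the t-test as a sensitivity analysis.
2. **Primary response difference.** Keep the unadjusted difference and its stated 21.2-point bound. Add, as supportive, a risk difference standardised over baseline diameter from a logistic model with arm and diameter, with a 90% interval by the delta method or bootstrap. This targets the same marginal difference.
3. **Randomisation.** State in Section 8.2 whether it is stratified, and by what.

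Use baseline diameter alone, without scan age. The cost is SAP wording and one degree of freedom. No new measurement is needed, because RECIST already requires the baseline diameter; the sponsor should confirm that the in-field value can be identified in the data. If the interim look has already been taken, the change can still be made but should be dated and labelled as made after it.

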Inclusion and exclusion criteria ^e	X									
Registration/Randomization (Phase 1/Phase 2) ^e	X									
Medical history (includes smoking history)	X									
Demography	X									
Complete PE including height and weight	X								X	
ECOG Performance Status	X								X	
Vital signs ^f	X	X	X	X	X	X				
PK Blood samples ^g		X	X							
12-lead ECG ^h	X	X		X						
AE/SAE review ⁱ		X	X	X	X	X	X	X	X	
Concomitant medications/treatments and smoking review ^j	X	X	X	X	X	X		X	X	X
Survival Status								X	X	X
Serum pregnancy test (WOCBP only)	X									
Serum chemistry panel	X						X			
Complete blood count	X						X		X	
PT/INR, aPTT	X									
PFTs – SpO ₂ , FEV1, FVC and DLCO ^{k, n}	X								X	
CT chest for pneumonitis scoring ^k	X								X	X
CT (chest, abdomen, pelvis) ^k	X								X	X
GC4711/Placebo IV infusion ^l		X	X	X	X ^l	X ^l				
SBRT administration ^m		X	X	X	X ^m	X ^m				

AE = adverse event, BP = blood pressure, CBC = complete blood count, CT = computed tomography, CTCAE = Common Terminology Criteria for Adverse Events, DLCO = diffusion capacity of lung for carbon monoxide, ECG = electrocardiogram, ECOG PS = eastern cooperative oncology group performance status, FEV1 = forced expiratory volume in 1 second, FU = Follow-up, , IV = intravenous, PE = physical examination, PET = positron emission tomography, PFTs = pulmonary function tests, PK = pharmacokinetics, SAE = serious adverse event.

- a Screening evaluations should occur within 21 days of Treatment Day 1, except where otherwise noted
- b The Day 12 visit should occur 7 days after the last dose of SBRT \pm 5 days
- c The 30- and 90- day post SBRT completion visits should occur on or within 7 days after target date and may be performed remotely via telemedicine visits. The Months 6 and 12 post SBRT completion visits should occur \pm 7 days of target date.
- d The Month 18 and 24 post SBRT visits should occur \pm 14 days of target date.
- e Registration/Randomization should occur after all screening assessments are performed, eligibility is confirmed, and within 7 days of the first dose of SBRT. Confirmation of eligibility should include confirmation of diagnosis, histology and exclusion of distant disease by standard practice.
- f BP and HR should be taken prior to each infusion, monitoring possible hypotensive symptoms, please repeat before going from infusion to radiation site.

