The RTOG 0813 trial identified SBRT dosing of 11.5 or 12 Gy x 5 fractions as associated with acceptable toxicity and with approximate 2-year rates for local control, overall survival, and progression-free survival of approximately 90%, 70%, and 55%, respectively ([Bezjak 2019](#)). Other studies ([Stone 2015](#), [Mohamad 2018](#)) reported control rates around 70% and PFS 50-60% at 2 years.

Radiation-induced lung injury is a slowly developing process, mostly manifesting as radiological changes only and transient symptoms around 4-6 months (mean 135 days) after treatment ([Jain 2018](#), [Ferrero 2015](#)). Clinically scored and symptomatic pneumonitis is seen in approximately 10% of patients 6 months after SBRT ([Kang 2015](#), [Yamashita 2014](#), [Mohamad 2018](#)). [Stone et al \(2015\)](#) referred to DLCO decline as the most objective measure of lung toxicity, referring to an observed decline (grade 1 or more) in 20-30% of patients. While a small decline is not seen as clinically significant, it is predictive for more severe accumulative toxicity risk in cases of pre-existing lung disease or in those with subsequent need for re-treatment in the thoracic area. Radiological changes in lung parenchyma are observed in over 40% of SBRT patients ([Kimura 2006](#), [Timmerman 2018](#)).

Approximately a 25% of patients experience declines in DLCO, reported after a 5-fraction regimen SBRT ([Stone 2015](#)). Slow decline in lung function and radiological changes are described after SABR/SBRT leaving a small portion of patients (mean 10%) with persistent significant decline at one year, which can be difficult to distinguish from recurrence ([Huang 2012](#)). Both lung function testing and radiographical changes are directly related clinical scoring at 3 months ([Tadasuke 2020](#)), explaining a gradual change from radiological to functional and finally clinical symptomatic SBRT complication related to dose and volume treated.

Both radiological and clinical data are needed to create future guidelines around lung SBRT ([Mohamad 2018](#), [Tadasuke 2020](#), [Palma 2013](#)). Complementary drugs such as GC4711 may add important value by increasing efficacy and reducing pneumonitis risk.

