4.2 Study Duration for Participants

The study duration for participants is expected to be approximately 25 months. This includes a 21-day screening period, a treatment period of approximately 5-10 days, and long-term follow-up for 24 months. All subjects are evaluated 30 days after SBRT and 6, 12, 18 and 24 months post-SBRT.

If a participant experiences progressive disease prior to 24 months post-SBRT completion, they will continue for survival follow-up until end of study (24 months following the last administration of SBRT). No additional tumor assessments will be required after progression; however, adverse events for long term radiation toxicities will continue through 12 months post SBRT completion and survival follow up will continue through 24 months post SBRT completion.

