7.1 Efficacy Assessments

Tumor Assessment (RECIST)

Staging imaging will be performed by CT scan according to the SoA. Tumor Response will be evaluated at each time point. Radiographic response will be measured according to RECIST 1.1 (Eisenhauer 2009). All imaging will be interpreted locally by the investigational site radiologist. The same method of imaging used at baseline must be used at each follow up evaluation for treatment response.

The number of subjects exhibiting PR, CR and PR+CR will be reported at Months 6, 12, 18 and 24.

RECIST 1.1 Tumor Response Evaluation Definitions of the criteria used to determine objective tumor response for target lesions (Eisenhauer, 2009)	
Complete Response (CR):	Disappearance of all target lesions. Any pathological lymph nodes (whether target or non-target) must have reduction in short axis to <10 mm.
Partial Response (PR):	At least a 30% decrease in the sum of diameters of target lesions, taking as reference the baseline sum diameters.
Progressive Disease (PD):	At least a 20% increase in the sum of diameters of target lesions, taking as reference the smallest sum on study (this includes the baseline sum if that is the smallest on study). In addition to the relative increase of 20%, the sum must also demonstrate an absolute increase of at least 5 mm. (Note: the appearance of one or more new lesions is also considered progression)
Stable Disease (SD):	Neither sufficient shrinkage to qualify for PR nor sufficient increase to qualify for PD, taking as reference the smallest sum diameters while on study.

Definitions for Response Evaluation

Progression-Free Survival

Progression-free survival (PFS) is defined as the time from the date of registration (Phase 1) or randomization (Phase 2), to first occurrence of local and/or regional NSCLC progression, distant metastases from NSCLC, second primary tumor, or death due to any cause, whichever occurs first. Patients without progression and who did not die are censored at their last evaluable tumor response assessment.

Local and Regional Control

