Overall Survival (OS) as well as duration of local and regional control will be analyzed using the same approach as PFS. For OS, patients who have not died as of the time of analysis will be censored the date last known to be alive. For duration of local and regional control, local enlargement, marginal failures, involved lobe failure, or local relapse will be considered failure events for local control. Regional failure with nodal progression (new lesions) in the mediastinum will be a failure event for regional control. Distant metastases from the index lung cancer or a second primary tumor are not considered local progression. Patients who die with lung cancer, but who do not have documented local progression will be considered non-failures for local progression and will be censored on the day of their death. Patients who die without progressive lung disease and have no documented local progression will be considered non-failures for local progression and will be censored on the day of death.

Distant-metastases rate will be summarized descriptively.

Exploratory Endpoints

All safety endpoints will be summarized descriptively including mean and mean change from baseline for continuous endpoints and n and percent for categorical endpoints.

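### The example PFS reading times (2, 4 and 6 months from randomisation) fall before almost every first follow-up CT, so PFS and local/regional control read there are biased upward

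*Combined protocol and SAP*

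**What the plan says.** **Clock and reading times.** Section 8.5 states: "All time to event endpoints will be measured from date registration (Phase 1) or randomization (Phase 2". PFS is to be compared by a hazard ratio and log-rank test and described by Kaplan-Meier curves, the median, and survival probability at "representative times (e.g. at 2, 4, 6, 4 etc. months". The repeated 4 is evidently a slip.

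**Events.** Section 7.1 (Definitions for Response Evaluation) counts local or regional progression, distant metastasis, second primary tumour, "or death due to any cause, whichever occurs first".

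**Other endpoints.** Section 8.5 adds: "Overall Survival (OS) as well as duration of local and regional control will be analyzed using the same approach as PFS". Patients who die without documented local progression "will be considered non-failures for local progression and will be censored on the day of their death".

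**Scans.** Section 4.2 says: "All subjects are evaluated 30 days after SBRT and 6, 12, 18 and 24 months post-SBRT". In Table 1, CT appears at screening and then only in the Month 6/12 and Month 18/24 columns. The 30- and 90-day visits have no CT and may be done by telemedicine. Footnote c: "The Months 6 and 12 post SBRT completion visits should occur" within 7 days either side of target; footnote d allows 14 days for Months 18 and 24. Footnote e puts randomisation within 7 days of the first fraction. Footnote k asks that suspected progression be confirmed with PET at 6 months.

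**The concern.** PFS time runs from randomisation, while the scan calendar runs from SBRT completion and opens at Month 6. A Kaplan-Meier curve built on scheduled scans stays high until the first scan and then steps down. All three example times lie before that step for nearly every patient. Read there, PFS is close to an overall-survival figure, with some progression found off schedule added. Local and regional control are biased upward too: they use the same approach, and deaths are censored, so almost nothing is left that could count as a failure.

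The endpoint is secondary and descriptive. However, section 8.1 says the efficacy data may be used in planning future studies, and a 6-month PFS rate is the kind of figure that would be carried forward.

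**Working it through.** The plan states no figure on this point, so there is none to reproduce. The check has four steps.

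**1. When does the Month 6 scan fall?** Inputs:
- Lag from randomisation to first fraction: 0-7 days (Table 1, footnote e).
- SBRT course: up to 10 calendar days, plus 3 (section 6.2) or plus 5 (Table 1, footnote m). Both were used; those two passages need reconciling.
- Visit window: 7 days either side of target.
- Six months = 182.6 days.

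On target, with five daily fractions spanning 4 days, the scan falls on day 182.6 + 4 + (0 to 7) = 187 to 194. No scheduled scan can precede 2 or 4 months.

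A Month 6 scan falls by 6 months from randomisation only if lag + course span + window deviation is zero or less. Assume all three are uniform. With a minimum span a (days) and a range of spans r, the probability is (7 - a)³/6 ÷ (7 × r × 14).

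| Course span (days) | Share of Month 6 scans by 6 months |
|---|---|
| 2-10 | (5³/6)/(7×8×14) = 20.83/784 = 2.7% |
| 2-13 | 20.83/(7×11×14) = 20.83/1078 = 1.9% |
| 4-10 | (3³/6)/(7×6×14) = 4.5/588 = 0.8% |
| 4-15 | 4.5/1078 = 0.4% |

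**2. Size for PFS (illustration).** Section 2.1 cites "2-year rates for local control, overall survival, and progression-free survival of approximately 90%, 70%, and 55%, respectively". Treat 55% and 70% as true and hazards as constant. The first-event hazard is λ = -ln(0.55)/24 = 0.0249 per month, so true PFS(6) = exp(-6λ) = 86.1%.

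Let s be the share of first events that are deaths. The documents do not give s. Its upper limit follows from the cited rates: at most 30% have died by 2 years and 45% have had a PFS event, so s ≤ 30/45 = 67%. The lower value of 20% is an assumption. The death hazard after progression, μ, is set so that 2-year OS = 70%:

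OS(t) = exp(-λt) + (1 - s)λ[exp(-μt) - exp(-λt)]/(λ - μ)

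With no scan before 6 months and no symptom detection, PFS as read equals OS(6), so the overstatement is OS(6) - PFS(6). If 30% of progressions are found by symptoms, multiply by 0.7.

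| s | μ per month | OS(6) | Overstatement | With 30% symptom detection |
|---|---|---|---|---|
| 20% | 0.0771 | 95.0% | 8.8 points | 6.2 |
| 50% | 0.0327 | 92.4% | 6.3 points | 4.4 |
| 60% | 0.0142 | 91.4% | 5.3 points | 3.7 |
| 67% | 0 | 90.7% | 4.6 points | 3.2 |

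The few scans that do fall before 6 months lower these values only slightly. For scale, the single-arm 90% half-width with 30 patients is 1.645 × √(0.861 × 0.139/30) = 10.4 points.

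**3. Size for local control.** With 90% at 2 years and a constant hazard, true control at 6 months is 0.90^(6/24) = 97.4%. With no scan before then it reads 100%, a shift of 2.6 points, or 0.7 × 2.6 = 1.8 with 30% symptom detection. Section 2.1 also mentions control of around 70% in other studies. The true 6-month value would then be 0.70^(6/24) = 91.5% and the shift 8.5 points (6.0 with 30% symptom detection).

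**4. When do the scan windows close?** Latest permitted scan, counted from the same month after randomisation:
- Months 6 and 12: 7 + 10 + (3 or 5) + 7 = 27-29 days, less than one month (30.4 days). Hence 7 and 13 months, with 1.4-3.4 days to spare.
- Month 18: 7 + 10 + (3 or 5) + 14 = 34-36 days, more than one month but less than two (60.9 days). Hence 20 months, not 19.

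Large simulations (1,000,000 patients per scenario) under the same model, with s at 20-50% and 0-30% symptom detection, gave PFS of 84.4-85.1% against a true 84.0% at 7 months, 72.7-73.4% against 72.3% at 13 months, and 61.6-62.8% against 60.8% at 20 months. The 7-month error is about 0.4-1.1 points.

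**The case against.** The strongest reply is that nothing has been committed. The times are examples, the list contains an obvious slip, section 8.5 says a more detailed SAP will follow and take precedence on analytic conventions, and the stated objective is comparison over 2 years. That stands and keeps the point minor. Still, this is the only guidance on reading times in the text, and it has to be edited anyway.

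The size is also open to challenge, fairly. The cited 55% is an observed rate from another trial whose scan schedule is not in the documents, yet the illustration treats it as the true curve. The death share, symptom detection, constant hazards and absence of dropout are assumptions. The whole range lies inside the 10.4-point half-width. The bias is systematic, however, and more patients would not remove it.

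The 7-month reading has little margin. If progression were dated at PET confirmation (Table 1, footnote k), some events could fall after it, so the dating rule must be stated.

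A reader might infer that the treatment comparison is compromised. The documents do not support that: the hazard ratio, log-rank test and full curve do not use the reading times, and both arms share one scan schedule. A reader might also infer that local control is badly distorted because it would read near 100%; at the cited 90% rate the true 6-month value is already 97.4%.

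**Conclusion.** The mismatch is established from the schedule alone: the 2- and 4-month readings precede every scheduled follow-up scan, and the 6-month reading precedes all but about 0.4-2.7% of them if timing is uniform. PFS and local/regional control read at these times are biased upward.

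The size is illustrative only: about 4.6-8.8 points for 6-month PFS with no symptom detection and 3.2-6.2 with 30%, and about 2-3 points for local control at the cited 90%. It rests on constant hazards, the cited 2-year rates taken as true, deaths as 20-67% of first events, and no dropout.

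OS does not depend on scans and is unaffected. This is a minor, worthwhile correction to a descriptive secondary summary and does not put the trial's conclusions in doubt.

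**What to change.** In section 8.5, replace the parenthesis in "representative times (e.g. at 2, 4, 6, 4 etc. months" with wording to this effect:

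> PFS and local/regional control probabilities will be reported at times from randomisation that fall after the Month 6, 12 and 18 scan windows have closed (for example 7, 13 and 20 months), with progression dated at the scan that first showed it even if PET confirmation comes later. OS will be reported at 6, 12, 18 and 24 months.

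If progression is instead to be dated at PET confirmation, use a later first reading, such as 8 months. The SAP should also define the 2-year PFS and local/regional control result so that it includes the Month 24 scan.

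The cost is one sentence in the protocol and one SAP definition, with no new visits or data. The reported landmark figures become slightly less favourable.
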